13. SUBJECT PAYMENT

Participants will receive \$25 for completion of each study visit (V1-V6) or up to \$150 in total at the completion of the study to help offset transportation costs and their time. Participant payments will be received via check requested from the Pennington Biomedical (LSU) payroll department or charging card in accordance with standard procedures.

A smartphone intervention for WIC mothers to improve nutrition and weight gain during pregnancy

"SmartMoms in WIC"

NCT04028843

PBRC IRB# 2018-039-PBRC

Version Date: May 17, 2024

*Finalized at 5/17/2024 research team statistical analysis meeting

Amendments to Statistical Analysis Plan

Prepared by [name] (Biostatistician)

In May of 2024, the research team met to go review the plan for statistical analysis. Several amendments were recorded to ensure the accuracy and transparency of our planned approach. No study data or unblinding information was used to inform these changes which are outlined below in detail.

Section 1.3

Amendment May 2024:

Wording clarification to ensure that gestational weight gain is expressed as incidence of appropriate study-observed GWG per week according to the 2009 Institute of Medicine guidelines, in addition to the three different measures, including study-observed GWG, weekly GWG, and deviation from guidelines.

Section 1.4

Amendment May 2024:

Details on prespecified subgroup analysis was moved from section 3 to this location to indicate these hypotheses were established a priori.

Section 1.4.1 and 1.4.2

Amendment May 2024:

Sections removed as they are not part of the primary analysis.

Section 2.1

Amendment May 2024:

The sample size was changed to enroll at least 330. The COVID-19 pandemic occurred in the early stages of data collection for the trial (i.e., 9 months after the first participants was screened). This resulted in several statewide restrictions, including lockdowns (with the initial "Stay at Home Order" issued on March 22nd, 2020), after 87 participants had been screened and 26 participants were in the primary data collection phase of the trial. Study visits were continued for participants who were already in the screening process or enrolled in the trial. It was necessary for visits to be modified to allow for collection of data to occur in a manner that ensured compliance with COVID-19 mandates (e.g., social distancing, wearing of PPE, etc.) for the participant and study staff. Restrictions required recruitment to cease for 5 months (March 2020 through July 2020). Research activities resumed when Louisiana progressed to Phase 2 of the reopening plan however, multiple restrictions were still in place that required adjustment of study procedures (detailed in the amended protocol). To adjust to and address the unforeseen circumstances arising from COVID-19 (including to comply with the time constraints set by the funding institute), the trial steering committee decided in October 2022 to end enrolment by December 2023. Based on trial enrolment through 2022, enrolment rate was estimated to be at least 11 participants per month for the following year, and as a result, it was assumed that the trial could achieve a sample size range of between N=339 and N=360. See below in section 2.3 for more details.

Section 2.2

Amendment May 2024:

The randomization section edited to denote that regions were used as the blocking information for the randomization scheme as compared to clinics since multiple clinics per regions were used for enrolment.

Section 2.3

Amendment October 2022:

The sample size was updated to a minimum of 330. The initial estimated effect size for the SmartMoms® intervention was based on preliminary data in the Expecting Success trial. The incidence of appropriate GWG for people with overweight was 12.3% for Usual Care versus 43.8% in SmartMoms®, and in people with obesity, it was 0% for Usual Care and 42.9% in SmartMoms®. However, the Expecting Success trial was not conducted in an exclusively underserved population, so we needed to conservatively estimate the SmartMoms® intervention effect to ensure this study would be well powered. The incidence of appropriate GWG for the Usual Care group was derived from individuals receiving WIC benefits in the 2013 Louisiana Pregnancy Risk Assessment Monitoring System data. The table below was created to show the incidences needed for 80% power in each of the BMI categories. All the estimates were tenable since they were lower than the SmartMoms® trial estimates. This study aimed for a total sample of 432 originally to allow for unknown variability that may have caused the observed rates to be different than the ones used for the power analysis. Sample size was reassessed in response to the COVID-19 pandemic. Based on the feasible recruitment estimates, the sample size was lowered to a minimum of 330. No new data were used to obtain the changes in power.

Table 1. Sample Size Estimates

BMI Category	Usual Care Appropriate GWG Incidence Rate	SmartMoms® Appropriate GWG Incidence Rate				
Normalweight	36.9	50.9	51.4	51.9	52.4	52.9
Overweight	23.9	37.9	38.4	38.9	39.4	39.9
Obesity	25.2	39.2	39.7	40.2	40.7	41.2
Overall	28.7	42.7	43.2	43.7	44.2	44.7
Sample Size		432	405	372	350	330

Section 3.0

Amendment May 2024:

Section was rewritten to clarify that treatment group differences within each BMI category is an apriori subgroup analysis we would consider.

Section 3.1

Amendment May 2024:

Description of methodology used to assess distributional assumptions was reduced to allow for which test is most statistically appropriate to be used.

Section 3.3

Amendment May 2024:

Based on recommendation from other statistical analysis experts in maternal health, a priori variable selection for determining covariates will be used. Gestational age at randomization, BMI category at randomization, and categorically defined parity will be the only covariates to be included in the model. Exploratory analysis will examine relationships of the outcomes with other

covariates. Variable section is now a priori, no variable section methods are needed. This section has been removed

Section 3.4 – removed now

Amendment May 2024:

Mediation and moderator section has been removed since these are intended to be exploratory analyses

Section 3.4

Amendment May 2024:

No missing data will be imputed, and the missing data section is adjusted accordingly. Data is missing not at random (MNAR) for participants that have early deliveries, and a sensitivity analysis will be conducted to include data from the visit during mid-pregnancy for individuals that had missing data at the late pregnancy visit time point. See section 4.1 for more details.

Section 3.6 – removed now

Amendment May 2024:

Details about how tables and figures will be expressed in tables have been removed to not limit how results can be presented in order to comply with journal guidelines.

Section 4.0

Amendment May 2024:

The description of the analysis was moved to this section as it was originally written for each individual hypothesis. There are no changes in analysis, but details were moved from this general analysis section to remove repetitive sections of the analysis descriptions.

Section 4.1

Amendment May 2024:

To better match the wording of the analysis that will be used, the details of intent-to-treat analysis approaches, including description of the included analysis populations were spelled out.

Section 4.2

Amendment May 2024:

Each of the study outcomes are explicitly defined to provide transparency and clarity on exact definitions.

Section 4.3.1 – now removed

Amendment May 2024:

Hypothesis analysis description was reduced since a general description of the analysis is written in section 4. No changes are made to the actual analysis.

Section 4.4 – now removed

Amendment May 2024:

Removed the secondary objective section since it is not part of the primary results.

Section 4.5 – now removed

Amendment May 2024:

Removed the mediator and moderator section since it is not part of the primary results.

Statistical Analysis Plan Prepared by [name] (Biostatistician)

1 INTRODUCTION

1.1 Preface

This study is developed to address an important public health issue; maternal obesity and gestational weight gain (GWG) and in a population that is most vulnerable to the societal influences of overconsumption of energy dense foods and sedentary behaviors. Capitalizing on the Louisiana Special Supplemental Nutrition Assistance, Women, Infants, and Children (WIC)'s unprecedented access to an economically disadvantaged and health disparate population, the overarching goal of this research is to adapt an innovative, patient-centred, pragmatic and scalable weight management intervention called SmartMoms® shown to foster healthy GWG, for dissemination to pregnant individuals served by WIC. If SmartMoms® is efficacious when embedded in the Louisiana WIC program, it will provide the first indication that WIC services could be expanded to meet an important public health need and serve as a conduit for delivering a scalable intervention to pregnant individuals across the country.

1.2 Purpose of the Analyses

The analysis will be conducted to test if the participants in the SmartMoms® group differ in terms of GWG as well as pregnancy and birth outcomes as compared to participants in the Usual Care group.

1.3 Study Aims and Endpoints

The overarching goal of the study is to test the effectiveness of SmartMoms®, a patient-centred, pragmatic and scalable intensive lifestyle intervention, to foster healthy GWG in low-income pregnant individuals in the WIC program, a health disparate, racially diverse and underserved population.

Hypothesis 1: The incidence of appropriate study observed GWG per week according to the 2009 Institute of Medicine guidelines [1] will be higher in the SmartMoms® group as compared to the Usual Care group.

Hypothesis 2: Study observed GWG seen in the SmartMoms® group will be less as compared to the Usual Care group. This will be assessed using the following three measures: study observed GWG, weekly GWG, and deviation from the 2009 Institute of Medicine guidelines.¹

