2.1. Hypotheses

Relative to WIC participants receiving Usual Care, participants receiving SmartMoms® will have a:

A: higher incidence of appropriate GWG according to the 2009 IOM guidelines

B: smaller deviation in GWG per week from the 2009 IOM guidelines

C: significant improvements in both physiological and behavioral factors including diet quality, physical activity, birth outcomes, postpartum weight loss, quality of life and mood and WIC food voucher redemption rates.

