2.2. Endpoints

Primary endpoint:

• Incidence of appropriate weight gain in pregnancy as defined by the 2009 IOM Guidelines [2].

Secondary endpoints:

- Rate of GWG per week
- Maternal diet (24h recall)
- Physical activity (Accelerometry, Pregnancy Physical Activity Questionnaire)
- Quality of life and stress (Depression Anxiety Stress Scales-21, Quality of Life Inventory, Household Chaos Questionnaire)
- Maternal and infant birth outcomes
- Infant feeding style (Infant Feeding Style questionnaire and Breastfeeding Questionnaire)
- WIC food voucher redemption rate
- Postpartum weight retention (measured 1, 6 and 12 months after delivery)

Exploratory endpoints: This study is also powered for a comparison of GWG between BMI categories. As an exploratory aim we will test whether maternal body mass index (BMI) is a moderator of intervention effects on GWG (relative to Usual Care).

Planned post-hoc analyses include testing moderators of intervention effects on GWG in BMI categories, race/ethnicity groups and in the SmartMoms[®] group only, intervention adherence.

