Overall deviation rates will be reported using a linear effect mixed model, using random effects to account for site and within-subject correlation. The response is the deviation of the weekly GWG rates from the IOM guideline rates. Models will be reported using both the simple model with treatment and BMI category and with covariates selected by LARS. Adjusted means of the deviations will be obtained using the least squared means. Two-sample t-test will be used to compare adjusted mean deviations.

Hypothesis C: Improvements in Physiological and Behavioral Factors

Each physiological and behavioral factor will be investigated independently from each other. Linear mixed effect models, like the ones listed in 2B, will be used to test differences between the treatment groups with least square

means. The response for each of these models will include both repeated measures and percent change from baseline approaches.

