4.2 Outcomes Measures

Per the 2009 Institute of Medicine guidelines,¹ each BMI category is allocated a different rate of GWG per week, which we will base our BMI-specific definition of GWG outcomes on (Table 4).

Table 4. 2009 Institute of Medicine Guideline Ranges for Weekly GWG

BMI Category	Inadequate	Adequate	Excessive	
Normalweight	< 0.35	0.35 kg/week to 0.50	>0.50	
_	kg/week	kg/week	kg/week	
Overweight	<0.23	0.23 kg/week to 0.33	>0.33	
_	kg/week	kg/week	kg/week	
Obesity	<0.17	0.17 kg/week to 0.27	>0.27	
-	kg/week	kg/week	kg/week	

Study observed GWG is defined as the difference between clinic weight assessed during late pregnancy and clinic weight assessed during early pregnancy.

Weekly GWG is defined as study observed GWG divided by the number of weeks between the early and late pregnancy study visits, with number of weeks calculated based on the number of days between study visits divided by 7.

Incidence of appropriate study observed GWG per week is defined as the number of participants that have weekly GWG in the adequate category according to the 2009 Institute of Medicine guidelines as opposed to inadequate or excessive (Table 4).

Deviation from the 2009 Institute of Medicine guidelines will be defined as the absolute difference in weekly GWG outside of the range bounds (Table 4). Participants within the bounds will not be included in this analysis.

Adverse perinatal outcomes will be abstracted from the birth certificate records obtained from the state. The Louisiana Electronic Event Registration System (LEERS) collects all official records related to birth and includes information from prenatal and delivery records. These records will be requested from the state by the study investigators using records related to participant, incident pregnancy, and participant-reported delivery information.

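### SAP Hypothesis 2 predicts less weight gain where the protocol predicts smaller deviation from the guideline, and no planned comparison would show excessive gain being replaced by inadequate gain

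*SAP*

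**What the plan says.** **Protocol.** Section 2.1 gives Hypothesis B as a "smaller deviation in GWG per week from the 2009 IOM guidelines". Section 12.3 follows it: "The response is the deviation of the weekly GWG rates from the IOM guideline rates". It does not say whether that deviation is signed or absolute. Section 2.2 lists "Rate of GWG per week" as a secondary endpoint and gives it no direction.

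**SAP.** Sections 1.3, 2.3.1 and 4.3 state Hypothesis 2 as "Study observed GWG seen in the SmartMoms® group will be less as compared to the Usual Care group", and section 1.3 continues: "This will be assessed using the following three measures: study observed GWG, weekly GWG, and deviation from the 2009 Institute of Medicine guidelines". No rule says which measure decides the hypothesis if they disagree. Section 1.3 gives the study's overall goal as fostering healthy gain, not lower gain.

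**SAP section 4.2.** Table 4 sets inadequate, adequate and excessive weekly gain for each BMI category. The Hypothesis 1 outcome is adequate gain "as opposed to inadequate or excessive (Table 4"). Deviation "will be defined as the absolute difference in weekly GWG outside of the range bounds (Table 4"), and women inside the range are left out of that analysis. Section 4.3 plans no separate comparison of inadequate gain between arms.

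**The concern.** Hypothesis B aims at a target range, so gain that is too low counts against the intervention just as gain that is too high does. The SAP wording replaces this with a direction. On two of the three measures a lower mean agrees with the hypothesis for every woman, including a normal-weight woman already below 0.35 kg/week.

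The other planned analyses protect only in part. A woman moved from adequate to inadequate lowers the appropriate-gain count, so Hypothesis 1 detects that move. A woman moved from excessive to inadequate is a failure before and after, so Hypothesis 1 does not change. If she ends about as far below the range as she would have been above it, the absolute deviation does not change either.

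The trial could therefore report a clearly lower mean gain, in the direction its SAP predicted, with no planned estimate showing how much of the reduction was a move below the range.

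**Working it through.** **Inputs.** From SAP Table 4: normal-weight range 0.35 to 0.50 kg/week, overweight 0.23 to 0.33, obesity 0.17 to 0.27. From SAP 2.3.1: 330 participants, 110 per BMI category, 15% attrition, a Hypothesis 2 difference of 0.16 kg/week, and 36.9% adequate gain in normal-weight Usual Care. Neither document gives an SD or an arm mean for weekly gain. The normal distribution, the means and the SD below are assumptions.

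**Step 1. The SAP's own power figure.** It cannot be reproduced directly without an SD, so the SD is back-solved. Evaluable women per arm within a BMI category: 110 × 0.85 / 2 = 46.75. For 80% power at two-sided 0.05, SD = 0.16 / [(1.96 + 0.84) × √(2/46.75)] ≈ 0.276. With 330 × 0.85 / 2 ≈ 140 per arm, overall power is then 99.8%, which agrees with the SAP's statement of over 99%. A lower mean gain is thus a result the trial is well placed to detect.

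**Step 2. Choice of SD.** Under a normal model the adequate proportion is largest when the mean is mid-range, where it equals 2Φ(0.075/SD) − 1 for normal weight. This is 38.3% at SD 0.15, 29.2% at SD 0.20 and 21.4% at SD 0.276. Reaching the SAP's 36.9% needs an SD of at most about 0.156. SD 0.15 is used below, and 0.276 is treated as an upper bound.

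**Step 3. A pure swap, normal weight.** Inadequate = Φ((0.35 − μ)/0.15); excessive = 1 − Φ((0.50 − μ)/0.15).

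| | Usual Care, μ = 0.505 | SmartMoms, μ = 0.345 |
|---|---|---|
| Inadequate | Φ(−1.033) = 15.1% | Φ(0.033) = 51.3% |
| Adequate | 33.6% | 33.6% |
| Excessive | 1 − Φ(−0.033) = 51.3% | 1 − Φ(1.033) = 15.1% |

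With a = (0.35 − μ)/σ and b = (0.50 − μ)/σ, the mean distance outside the range over all women is (0.35 − μ)Φ(a) + σφ(a) + (μ − 0.50)(1 − Φ(b)) + σφ(b). For Usual Care this is 0.012 + 0.062 = 0.074. Among out-of-range women it is 0.074 / 0.664 = 0.11 kg/week. By symmetry SmartMoms gives the same values. Hypothesis 1 and deviation are both null, while weekly gain is lower with 99.9% power in this stratum alone (47 per arm).

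**Step 4. Calibrated to the SAP's 36.9%.** With SD 0.15, a Usual Care mean of about 0.468 gives 36.9% adequate. A shift of 0.10 kg/week, to 0.368, moves inadequate gain from about 22% to 45% and adequate gain from 36.9% to about 36%.

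**Step 5. Range.** Repeating the mirrored 0.16 kg/week shift over SD 0.10 to 0.277, inadequate gain goes from 6–29% to 51–52% in normal weight, and from 10–32% to 54–62% in overweight and obesity. Adequate gain is unchanged by construction.

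**Step 6. Where Hypothesis 1 does respond.** With Usual Care at mid-range (0.425) and SmartMoms at 0.265, adequate gain falls from 38.3% to 22.7% and inadequate gain rises from 30.9% to 71.5%. Hypothesis 1 moves against the intervention, while total and weekly gain still agree with Hypothesis 2.

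**Step 7. The same cases with deviation scored in all women (0 if in range).** Step 3 gives 0.074 in both arms, correctly no benefit. Step 6 gives 0.059 against 0.116 kg/week, which reads as harm.

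**The case against.** A reader might infer that the SAP would declare the intervention successful on lower gain alone. The documents do not say so. Hypothesis 2 states an expected direction, and no section sets a success rule for it. Hypothesis 1 comes first, matches the protocol's only primary endpoint and treats inadequate gain as failure. SAP section 3 says that unadjusted secondary results should not be used to infer definitive effects. That protection is not complete, because section 1.5 calls the objectives above it primary, which leaves the rank of Hypothesis 2 unclear.

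A reader might also infer that nothing in the plan catches women pushed out of the adequate range. That is wrong: Hypothesis 1 catches them, as Step 6 shows. Only the swap of excessive for inadequate gain escapes. Nor is a one-sided test specified; SAP section 1.2 speaks of whether the groups differ.

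Other provisions help in part. SAP section 3.5 promises percentages for categorical levels, which may yield inadequate and excessive counts but not a between-arm estimate. Small for gestational age is an exploratory comparison. Protocol 11.2.3 raises alerts for weight loss, which is not the same as low gain. Both hypotheses are already analysed within BMI category.

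The pilot data also favour the sponsor's expectation. In overweight and obese women, mean gain was above the recommended rate in both arms (protocol 12.2: 0.21 and 0.16 kg/week above it in Usual Care, 0.06 in SmartMoms), so lower gain moved the mean toward the range. No pilot figures are given for normal-weight women. Finally, the protocol does not define its own deviation as absolute, and a signed version would share the weakness.

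These points limit the seriousness. They do not remove the mismatch in direction or supply the missing comparison.

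**Conclusion.** The concern holds in a limited form. SAP Hypothesis 2 departs from protocol Hypothesis B by predicting less gain, and two of its three measures take no account of the guideline range. The primary hypothesis guards against loss of adequate gain but not against excessive gain being exchanged for inadequate gain, and the deviation measure can miss that exchange too.

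In the illustrations inadequate gain rises by 36 points (51.3 − 15.1) with adequate gain constant, or by about 23 points (45 − 22) with adequate gain almost constant. Both rest on a normal model with SD 0.15 and assumed means. They show what the wording allows and do not forecast the result. The primary analysis and the sample size are unaffected. The sponsor should make the change because it alters what can be concluded from a lower mean gain.

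**What to change.** 1. Restate Hypothesis 2 in SAP sections 1.3, 2.3.1 and 4.3 as smaller absolute deviation of weekly gain from the Table 4 range, and change section 4.2 so that all participants with a weekly gain are included, scored 0 if in range. Rewording without keeping in-range women would rest the hypothesis on a subset defined by the outcome.
2. Report total and weekly gain as two-sided estimates with confidence intervals and no benefit direction.
3. Add between-arm comparisons of the proportion below and the proportion above the Table 4 range, overall and by BMI category, with confidence intervals from the Hypothesis 1 logistic model. State that they are read alongside any difference in mean gain.

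A rule barring any claim of benefit whenever inadequate gain increases should not be added. Under this model every downward shift raises inadequate gain. With the mean going from 0.55 to 0.45 at SD 0.15, adequate gain improves from 27.8% to 37.8% and excessive gain falls from 63.1% to 36.9%, yet the rule would apply because inadequate gain rises from 9.1% to 25.2%.

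Cost: SAP wording and two extra models on data already collected, with no change to sample size or visits.
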